## 1 Schema

Visit Number	1	2	3	4	5	6
Time of Visit	Day 1	Week 2	Week 4	Week 6	Week 8	Week 14
Inclusion/Exclusion Criteria	X					
Informed Consent	X					
Investigator Evaluation	X	X	X		X	X
Patient Evaluation					X	X
Dispense 4% Hydroquinone, Cleanser, Sunscreen	X					
Salicylic Acid Peel	X	X	X	X		
Adverse Events	X	X	X	X	X	X

## 2 Study Objectives

To assess the efficacy of salicylic acid peels every two weeks in combination with 4% hydroquinone versus 4% hydroquinone alone in the treatment of melasma in Hispanic women. This study will take place over 14 weeks in which time all patients will use 4% hydroquinone cream to the affected areas twice daily, but half the face will receive four salicylic acid peels every two weeks. End points include change in pigmentation of skin affected by melasma compared to normal skin measured objectively with a mexameter and subjectively by the MASI score, the melasma severity assessment, and the physician and patient global evaluation.

## 3 Background

Melasma is a common disorder of hyperpigmentation affecting the cheeks, forehead, and upper lip. It manifests as tan-brown macules/patches slowly enlarging on the face. It can affect all racial types but predominately affects women of skin types IV-VI especially those living in areas of intense UV radiation (1).

The exact etiology of melasma is unknown, but it is thought to be multifactorial. Known triggers/exacerbators include pregnancy, hormone therapy, and sunlight. Melasma can be very difficult to treat and often frustrating for the patient and physician. A recent study has shown in Hispanic women that melasma significantly affects quality of life in both personal and professional aspects (2).

Conventional treatments thus far include elimination of causative factors and a hypopigmenting agent, typically 4% hydroquinone either alone or in combination with a

retinoid, topical steroid or superficial peeling agents. In addition, patients are advised to use a sunscreen and take other sun protective measures (1).

Patients with melasma may significantly benefit from the addition of biweekly salicylic acid peels to 4% hydroquinone cream. A previous, uncontrolled study showed that salicylic acid peels of 20% to 30% at two week intervals in patients with skin types V-VI resulted in moderate-significant improvement in melasma in 4 of 6 patients with melasma (3). Although hydroquinone is the standard of care for melasma, no controlled trials have been performed comparing the efficacy of salicylic acid peels in combination with 4% hydroquinone versus hydroquinone alone.

#### **4 Agents**

The two agents used in this study will be salicylic acid 20-30% peels and 4% hydroquinone cream, both of which are FDA approved for melasma.

The 4% hydroquinone cream will be purchased as a generic cream formulation. Patients will apply this cream twice a day to affected areas on both sides of the face. Contraindications to the use of 4% hydroquinone include pregnancy, plans for pregnancy, or breast feeding (in all cases patients will be excluded from our study). Side effects can include irritation, redness, pruritus, and hypo/hyperpigmentation. One study comparing the use of 4% hydroquinone with placebo found no significant difference between the two groups in terms of incidence of side effects (4).

The salicylic acid peels will also be purchased from a medical supply company in both 20% and 30% concentrations. Patients will receive 4 peels total at 2 week intervals. The first two peels will be 20% and the last two peels will be 30%. Side effects may include redness, irritation, pruritus, skin peeling, and hypo/hyperpigmentation. One study looked at the safety and efficacy of salicylic acid peels in darker racial-ethnic groups and found the above mild side effects to occur in ~16%, all of which were transient, resolving in less than two weeks (3).

#### **5 Eligibility Criteria**

Consenting Hispanic women with bilateral moderate-severe epidermal or mixed melasma will be enrolled in this study. This study will be limited to only Hispanic women due to the high frequency of melasma in this population and in order to study a uniform population. Spanish

speaking patients will be eligible for this study and a Spanish consent/HIPAA forms will be provided to them. In addition, someone who speaks Spanish will always be available to answer questions. Key exclusion criteria include pregnancy, breastfeeding an infant, use of 4% hydroquinone cream within three months of the study, and history of chemical peels, microdermabrasion, or facial laser treatment within 9 months of the study.

## **6 Material and data to be accessioned**

Thirty adult Hispanic women with moderate to severe melasma, diagnosed by clinical criteria, will be recruited to participate in this study. Accounting for ~ 10 screening failure, we hope 20 patients will be able to complete this 14 week prospective investigator blinded, split-face trial of biweekly salicylic acid peels in combination with 4% hydroquinone versus 4% hydroquinone alone.

At the initial visit, patients will be asked for their past medical history, current medications, and will undergo a urine pregnancy test. Once it is determined that patients are eligible for the study, they will be asked to give informed written consent and sign a HIPAA authorization. Next they will undergo evaluation of their melasma by the study investigator which includes an objective measurement of the darkness of their melasma by mexameter (an electronic device which painlessly measures skin pigmentation, 0-white, 1000-black, by placing a probe on the skin) compared to nearby normal skin. In addition, a MASI score will be calculated (a subjective score based on darkness, area of involvement, and homogeneity of the pigment). A melasma severity assessment will also be performed by the physician which rates the severity of the melasma on each of side of the face according to the following numerical scale: 0 for clear, 1 for mild, 2 for moderate, 3 for severe. Standard and polarized photographs (a specialized photograph that enhances the appearance of hyperpigmentation) will also be taken. Patients will then undergo a 20% salicylic acid peel to half the face (side to be peeled will be determined by a computer generated randomization code). In addition they will be given 4% hydroquinone to use on the affected areas twice a day (X 14 weeks) and a cleanser and sunscreen to be used daily. No other medications for melasma will be allowed during the study period.

At week 2, patients will undergo another 20% salicylic acid peel to half the face. They will be asked to report any adverse events from the salicylic acid peels or the hydroquinone. Prior to the peel a mexameter reading will be taken and the MASI score calculated for each side of the face.

At week 4 and 6 patients will undergo 30% salicylic acid peels and be asked to report any adverse events. In addition, the study investigator will take mexameter readings from the peeled/unpeeled sides and calculate a MASI score on both the peeled/unpeeled sides at week 4 (investigator will be blinded as to which side was peeled). At weeks 8 and 14, patients will report any adverse events and the study investigator will take mexameter readings and calculate a MASI score as above. The physician will also perform a melasma severity assessment for each side of the face at weeks 8 and 14. In addition, at 8 and 14 weeks, both the physician and patient will perform a subjective global evaluation of which side, if any, had more improvement in the following terms: no change/slight/moderate/marked.

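### Section 6 puts history taking, medication review, a urine pregnancy test and the eligibility decision before informed consent and HIPAA authorisation

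*Combined protocol and SAP*

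**What the plan says.** Section 6 (Material and data to be accessioned) sets out visit 1 as a sequence:

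- First, screening: "At the initial visit, patients will be asked for their past medical history, current medications, and will undergo a urine pregnancy test".
- Then consent: "Once it is determined that patients are eligible for the study, they will be asked to give informed written consent", with the HIPAA authorisation signed at the same point.
- Then baseline assessment: "Next they will undergo evaluation of their melasma by the study investigator". This covers mexameter, MASI, the physician's 0 to 3 severity grade and photographs.
- Then the first peel, on the side given by the randomisation code.

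Section 5 (Eligibility Criteria) lists pregnancy among the key exclusions, and Section 4 repeats that pregnant women are excluded. Section 5 also provides for consent and HIPAA forms in Spanish. The schedule tables in Sections 1 and 6 place both the inclusion/exclusion check and consent on Day 1, with the inclusion/exclusion row above the consent row. Neither table states an order within the visit.

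**The concern.** Consent and authorisation protect a participant only if they are sought before the research procedure or the collection of her information. Here the protocol requires both, and arranges for them in the participant's language, but places them after a urine test whose result is needed to apply a trial exclusion.

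The order affects every woman who comes to visit 1. For a woman who passes screening, consent arrives late. For a woman who fails on history, medications or the pregnancy test, it does not arrive at all, because only women already found eligible are asked. That cannot be put right afterwards for those women. The matter concerns conduct and participant protection, not the analysis.

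**Working it through.** The protocol gives no figure that needs reproducing. The check is a reading of the sections against one another, followed by one bound.

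**1. Is the order really an order?** Yes. In Section 6 the consent sentence is conditional on eligibility having been determined, and the following sentence opens with *Next*. This is a sequence, not a loose list of visit 1 activities.

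**2. Does anything placed before consent belong to the study?** Yes, at least the pregnancy test. Section 5 makes pregnancy a key exclusion, and the test appears immediately before the eligibility decision. History and medications feed the other exclusions in Section 5 (recent hydroquinone use; recent peels, microdermabrasion or facial laser treatment).

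**3. Does another section cure it?**

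| Place | What it says about consent | Does it move consent earlier? |
|---|---|---|
| Section 1 table | Day 1, listed below inclusion/exclusion | No |
| Section 5 | "Consenting Hispanic women with bilateral moderate-severe epidermal or mixed melasma will be enrolled in this study" | No; it governs who is enrolled, not who is screened |
| Section 6 text | After the eligibility decision | This is the problem |
| Section 6 table | Day 1, listed below inclusion/exclusion | No |
| Section 10 (Registration and study monitoring) | Nothing | No |

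No section mentions a separate screening consent, a waiver or an authorisation obtained beforehand.

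**4. How many women?** Inputs, both from Section 6: 30 recruited and about 10 screening failures.

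- Tested and questioned before consent: all who are screened. This needs no assumption beyond the stated order.
- Never asked for consent: those who fail before consent. If every expected failure occurs there, 10/30 = 33%. If none does, 0/30 = 0%. Section 6 does not say when or why women are expected to fail, so the range is 0 to about 10 of 30.

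**5. Does any statistical quantity change?** No. The primary comparison in Section 11 is the difference between affected and nearby normal skin on the mexameter, peeled against unpeeled side. Baseline measurements, randomised side and first peel all follow consent already, and moving consent to the front leaves them unchanged.

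**The case against.** Several replies have force.

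- *History and medication review may be routine clinic care.* Possibly, though the protocol does not describe them so. The reply does not reach a pregnancy test performed to apply a trial exclusion.
- *The consent form may address screening.* The form was not available for this reading. A form signed after the test still cannot authorise it beforehand, and a woman who fails screening would not be given it.
- *Nobody is treated without consent.* This is correct. The melasma evaluation, photographs and peel all come after consent, which limits the harm to the screening step.
- *Nothing says that data on women who fail are kept.* This also stands. Section 6 says that patients are asked about history. Section 10 describes recording in the report forms in the context of women who have been recruited and have completed the initial evaluation. A reader might infer that screening-failure data are recorded and held without authorisation, but the text does not say so.

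A reader might also infer a second fault in the same sequence. Eligibility requires bilateral moderate to severe disease, yet the physician's grade, which "rates the severity of the melasma on each of side of the face", is taken after eligibility is declared, so a woman graded mild on one side could be randomised. The documents do not support this as an error. Section 5 names no scale or cut-off. Section 6 says that the women recruited are diagnosed on clinical criteria, which allows a clinical judgement before consent. The 0 to 3 grade is an efficacy outcome: an end point in Section 2, a secondary assessment in Section 8 and an analysed variable in Section 11. Taking a baseline outcome after consent is proper. What remains is missing detail: the protocol does not say how or when the bilateral severity criterion is judged.

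**Conclusion.** The point holds for the order of consent. Section 6 states a rule, and the rule is wrong: a study-specific pregnancy test, the collection of health information and the eligibility decision all precede written consent and HIPAA authorisation, with no provision elsewhere that excuses it. It should be corrected before the protocol is used.

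All screened women are affected by the late consent. Those never asked number at most about 10 of 30 (33%). That is an upper bound, not an estimate: it assumes that the 30 counts women entering visit 1 and that every expected failure occurs before consent.

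The conclusion does not extend to the severity grading. The 0 to 3 grade is not an entry criterion anywhere in the protocol, and no loss of precision or bias from it has been shown. No estimate, significance level, power or sample size depends on this point.

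**What to change.** Rewrite the visit 1 paragraph of Section 6 in this order:

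1. Written informed consent and HIPAA authorisation.
2. Medical history, current medications and urine pregnancy test.
3. Confirmation of eligibility.
4. Baseline measurements: mexameter, MASI, severity assessment and photographs.
5. Side to be peeled, from the randomisation code.
6. First peel.

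For consistency, the consent row can be moved above the inclusion/exclusion row in the Section 1 and Section 6 tables. That is presentational, since the tables set no order within the day.

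Optionally, the sponsor may add a sentence saying how and when the bilateral moderate to severe criterion is judged. This should not be done by silently making the 0 to 3 grade an entry threshold. That would be a new inclusion rule, and it could raise screening failures in a plan that already expects about 10 among 30.

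The cost is a wording amendment. Every step already takes place at visit 1, so no visit, procedure or staff is added. The small downside is that consent is also obtained from women who then fail screening.

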### Visit Schedule and Assessments

Visit Number	1	2	3	4	5	6
Time of Visit	Day 1	Week 2	Week 4	Week 6	Week 8	Week 14
Inclusion/Exclusion Criteria	X					
Information & Informed Consent	X					
Investigator Evaluation	X	X	X		X	X
Patient Evaluation					X	X
Dispense Hydroquinone 4%, cleanser, sunscreen	X					
Salicylic Acid Peel	X	X	X	X		
Adverse Events	X	X	X	X	X	X

## 7 Treatments

### Investigational Therapy and Reference Therapy

Investigational Agent – salicylic acid peels (20-30%) applied every two weeks for a total of four peels

Reference Therapy – hydroquinone 4% cream applied BID X 14 weeks.

### Treatment Assignment, Blinding, and Randomization

Patients will all be given 4% hydroquinone to use on the affected areas for 14 weeks. In addition, each patient will receive biweekly salicylic acid peels to half of the face for a total of four peels (at week 0, 2, 4, 6). The first two peels will be 20% salicylic acid and the last two peels will be 30% salicylic acid. The side to be peeled will be determined by a computer generated randomization code. Only the investigators will be blinded in the study, due to the

nature of the treatments it will not be possible for the patients or the nurse performing the peels to be blinded.

No concomitant therapy will be allowed for the duration of the study. Patients who were already on an oral contraceptive pill will be allowed to continue the pills during the study, but oral contraceptive pills may not be introduced during the study.

### **Interruption or Discontinuation of Treatment**

Every patient has the right to discontinue study participation at any time, and every patient may be discontinued from the study for any reason beneficial to his/her well being. All data generated up to the time of discontinuation from the study will be analyzed and the reason(s) for discontinuation will be recorded.

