## **8 Evaluation Criteria**

Patients satisfying inclusion criteria will be chosen to participate in the study. The degree of pigmentation will be noted at baseline by mexameter readings taken on both sides of the face on affected skin and also nearby normal skin. Additional mexameter readings will be taken at weeks 2, 4, 8, and 14. In addition standard and polarized photographs will be taken at baseline and at weeks 8 and 14. A MASI score will also be calculated at baseline and at weeks 2, 4, 8, and 14. A melasma severity assessment will be performed by the physician at baseline and at weeks 8 and 14. A physician and patient global assessment will be performed at weeks 8 and 14, a subjective measure of which side, if any, improved more and to what degree (no change/slight/moderate/marked). Primary efficacy assessment will be improvement of melasma using mexameter readings while secondary assessment will be improvement in MASI scores, melasma severity assessment, and physician and patient global improvement compared with the opposite side.

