## **11 Statistical Considerations**

Investigators will enter the information required by the protocol into the Study Report Forms (SRFs). Additionally, a series of standardized photographs will be taken of each patient at baseline and 14 weeks to provide permanent documentation.

The objective of this trial is to study the efficacy and tolerability of salicylic acid peels in the treatment of melasma in Hispanic women. The data will be summarized with respect to efficacy and safety observations. Data will be presented for the complete intent-to-treat population (all patients having taken at least one dose of study medication) as well as the per-protocol population (all patients who completed the study without major protocol deviations).

The assessment of safety will be based mainly on the frequency of adverse events, which includes all serious adverse events. Adverse events will be summarized by presenting for each treatment group the number and percentage of patients having any adverse event, having an adverse event in each body system, and having each individual adverse event. Any other information collected (e.g. severity or relatedness to study medication) will be listed as appropriate.

Efficacy will be primarily assessed by comparing delta mexameter readings (affected skin-nearby normal skin) on the peeled versus unpeeled side. This data will be analyzed using a two factor repeated measures analysis of variance. Efficacy will be secondarily assessed by change in MASI score on the peeled versus unpeeled side also using the repeated measures analysis of variance. Another secondary measure of efficacy will be the melasma severity assessment of the peeled versus unpeeled side also using the repeated measures analysis of variance.

A McNemar chi-squared test will be used to determine if there is agreement between the Physician and Patient Global Assessment of Improvement at 8 and 14 weeks as to which side appears more improved. For those in which there is agreement, we will further look at the degree of agreement and use the McNemar chi-squared test to see how well they correlate. The critical value for all efficacy, tolerability, and subject satisfaction survey analyses will be 0.05.

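### Section 7 promises to analyse all data up to discontinuation, but the repeated measures ANOVA in Section 11 is not specified well enough to deliver it; a mixed model on all observed readings would

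*Combined protocol and SAP*

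**What the plan says.** Section 7 (Interruption or Discontinuation of Treatment) commits that "All data generated up to the time of discontinuation from the study will be analyzed".

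Section 11 makes a second commitment. Results are to be shown for the "complete intent-to-treat population (all patients having taken at least one dose of study medication") and, separately, for the "per-protocol population (all patients who completed the study without major protocol deviations").

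For the primary outcome, the affected-minus-normal mexameter delta on each side of the face, Section 11 says: "This data will be analyzed using a two factor repeated measures analysis of variance". The first secondary outcome is "change in MASI score on the peeled versus unpeeled side also using the repeated measures analysis of variance", and the severity assessment is given the same method.

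Section 8 sets the visits. After the baseline reading, "Additional mexameter readings will be taken at weeks 2, 4, 8, and 14"; MASI follows the same times. For severity, "A melasma severity assessment will be performed by the physician at baseline and at weeks 8 and 14".

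On numbers, Section 6 recruits thirty women and says: "Accounting for ~ 10 screening failure, we hope 20 patients will be able to complete". The last paragraph of Section 11 describes a pilot of about 20.

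The documents do not state the two factors of the ANOVA (presumably side and visit), the covariance structure, the method of estimation, or what happens to a patient with some visits missing.

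**The concern.** Defining a population says who belongs to the analysis. It does not say how a patient with two or three of five visits enters the model, and the method named in Section 11 covers forms that treat such a patient in opposite ways.

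- **Balanced form.** It needs every side-by-visit cell. A patient without week 14 is removed entirely, including the readings already taken. The Section 7 commitment would fail for efficacy (adverse event summaries could still use these patients), and the intent-to-treat efficacy result would come close to the completers' result that Section 11 plans to show separately.
- **Patient as a block.** All observed readings are used. But the patient effect is fixed, so a leaver's last poor readings are in effect carried forward in full. If patients leave because of a recorded worsening on one side, the side contrast at week 14 can be over-corrected.

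Withdrawal linked to outcome is plausible here. Section 9 lets the investigator end participation if the patient's condition worsens or unexpected side effects occur, and only one side of the face is peeled. At stake are readings from a sample of about 20, for which Section 6 states no dropout allowance beyond screening failures, and possibly a shift in the primary contrast.

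**Working it through.** **The plan's own figure.** Section 6: 30 recruited − about 10 screening failures = 20. This reproduces. There is no power or effect-size calculation to reproduce.

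**Assumptions.** The documents give no dropout rate, SD, correlation or effect size, so every rate below is assumed. I take 20 as the number starting treatment, in line with the end of Section 11. Section 6 can instead be read as 20 completing, and the retention counts would then not follow.

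**Cells per patient.** Mexameter and MASI: 5 visits × 2 sides = 10. Severity: 3 visits × 2 sides = 6.

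**Patients kept by the balanced form.** With a probability m of missing each post-baseline visit, independently, the number kept is 20 × (1 − m)^k, where k = 4 for mexameter and MASI and k = 2 for severity.

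| m | Mexameter, MASI | Severity |
|---|---|---|
| 2% | 20 × 0.98⁴ = 18.4 | 20 × 0.98² = 19.2 |
| 5% | 20 × 0.95⁴ = 16.3 | 20 × 0.95² = 18.1 |
| 10% | 20 × 0.90⁴ = 13.1 | 20 × 0.90² = 16.2 |

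**Readings discarded by the balanced form.**

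- 4 of 20 leave after week 4: collected 16 × 10 + 4 × 6 = 184 deltas; used 160; lost 24/184 = 13%.
- 4 of 20 lack only week 14: collected 16 × 10 + 4 × 8 = 192; used 160; lost 32/192 = 17%.

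On simulated data of these two shapes, one balanced routine (AnovaRM in statsmodels) stopped with an error because the data were unbalanced. An ANOVA with patient as a block used all 184 and 192.

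**Bias among completers, closed form.** Suppose the worst fraction p on the peeled side leaves, with correlation ρ between visits (constant) and r between sides. The week 14 side difference among completers is then shifted by

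bias = ρ × √((1 − r)/2) × φ(z)/(1 − p), in SD of the side difference,

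where z is the normal quantile for p and φ the normal density.

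- p = 5%, ρ = 0.5, r = 0.7: 0.5 × 0.387 × 0.109 = 0.021.
- p = 20%, ρ = 0.7, r = 0.3: 0.7 × 0.592 × 0.350 = 0.145.

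Large simulations (400,000 patients per setting), which also allowed correlation to decay over visits, gave 0.01 to 0.15 in absolute value for a one-sided trigger. The sign favours the peel if peeled-side worsening drives withdrawal and goes against it if unpeeled-side worsening does. If worsening on either side triggers withdrawal, the bias is within 0.003 of zero with no true peel effect, and −0.005 to −0.11 (against the peel) with an assumed benefit of 0.5 to 1 SD of a single-side change.

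**Comparison of methods at 20 patients.** Four leave after a recorded week 4 worsening on the peeled side; no true effect; assumed correlations. Week 14 bias in SD of the side difference:

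| Analysis | Bias |
|---|---|
| Completers only | +0.08 to +0.11 |
| ANOVA, patient as a block | −0.03 to −0.06 |
| Unstructured likelihood-type fit on the side difference | within 0.003 |

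Other correlations would shift the first two rows.

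**Limits of the mixed model.**

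- With a random intercept only, bias was within 0.002 under constant correlation but up to 0.03 under decaying correlation.
- If the worsening comes after the last recorded visit, 0.003 to 0.076 remained, against 0.011 to 0.140 for completers: reduced, not removed.
- These checks cover bias of the estimate, not the behaviour of the small-sample test.

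**Scale.** The standard error of a mean side difference at 20 patients is 1/√20 = 0.22 SD. The largest bias, 0.15, is below it.

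**The case against.** The strongest reply is that no conflict has been shown. Nothing in the documents names a complete-case fit, and two statements point away from it: the Section 7 commitment and the intent-to-treat definition in Section 11. An ANOVA with patient as a block fits the wording and uses every reading. A routine that refuses unbalanced data does not silently drop patients; it forces a choice, which Sections 7 and 11 would then guide. This stands. A reader might infer that Sections 7 and 11 contradict each other, or that the balanced form is the intended or usual one. The documents support neither.

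A second reply is that the sizes are all assumed and modest. The largest bias needs the worst 20% on one side to leave without exception, Section 9 expects mainly minor adverse events, and this is a pilot. This also stands. A reader might infer that the trial will overstate the benefit of the peel; with the side behind withdrawal unknown, the documents fix neither direction nor size.

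A third reply is that a mixed model with 15 covariance parameters is ambitious for about 20 patients. That is fair as a caution on the choice of structure.

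What does not stand is that a sentence saying all readings are used would be enough. The block ANOVA meets that sentence and was still biased in the check above. Nor does pilot status remove the point: Section 11 applies a 0.05 critical value to all efficacy analyses.

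**Conclusion.** The point holds as a gap in specification for which a better method is available. Section 11 does not ensure that the named analysis honours Section 7 or its own intent-to-treat definition. One form of it would discard leavers' readings; the other keeps them but can mislead when withdrawal follows an observed worsening.

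The actual size is unknown. As an illustration with 4 of 20 leaving early, 13% to 17% of collected mexameter deltas would be lost under the balanced form, and completer bias would be at most about 0.15 SD of the side difference, less than one standard error. These figures rest on assumed dropout, correlations and withdrawal triggers, and on 20 patients starting treatment. The change should be made because it is cheap and settles the choice before the data are seen, not because serious bias has been demonstrated.

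**What to change.** In Section 11:

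1. For mexameter and MASI, replace the repeated measures ANOVA with a likelihood-based linear mixed model (side, visit, side-by-visit) on all observed readings from every treated patient. One workable form models the peeled-minus-unpeeled difference at each visit. An unstructured covariance over 5 visits then needs 5 × 6/2 = 15 parameters. Name in advance a structure that about 20 patients can support, and a small-sample correction such as Kenward-Roger.
2. Keep the complete-case result for the per-protocol set.
3. State that the severity analysis also uses all observed readings.
4. State that the model removes bias from withdrawal only if withdrawal depends on readings already observed and the covariance structure is adequate.

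The cost is a few sentences and slightly more analysis work, with no new visits or patients. A patient-block ANOVA should not be listed as an equal alternative.
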